6.0 Number of Subjects

We will enroll approximately 110 patients in this study to include 55 patients for each randomized ‘treatment’ group. Please refer to section 12.0 for the justification behind this enrollment number.

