10.0 Study Design / Methods

Once it is confirmed that the attending anesthesiologist has both examined the patient and decided on an anesthesia plan that aligns with our inclusion criteria, the patient and their family will be consented. If the patient is included in the study, the study member will randomize the patient to one of two groups: Group A - povidone-iodine ophthalmic solution, or Group B - ophthalmic balanced salt solution. This randomization will be determined using a simple randomization scheme provided by the study's statistician. All decisions regarding anesthesia care, including the indication for preoperative pharmacologic anxiolysis, will be made by the attending pediatric anesthesiologist. The case will then progress as it would without study involvement and the patient would be brought into the operating room and anesthesia would be administered. The standard of care course of anesthesia includes:

- Inhalation induction with oxygen in sevoflurane
- Insertion of a peripheral intravenous catheter after induction of anesthesia
- After a suitable depth of anesthesia is achieved, a laryngeal mask airway of an appropriate size will be inserted and secured

The only deviation from standard of care during the above process is the collection of data after induction, just prior to IV insertion. These data points are heart rate (HR), blood pressure (BP), respiratory rate (RR), arterial oxygen saturation (SaO₂), end tidal CO₂ (ETCO₂), inspiratory sevoflurane (InspSevo), and expiratory sevoflurane (ExpSevo). This data will be collected by a study member in real, intraoperative time. The collection of data will not affect the progression of standard anesthesia practice, as the data collector will not be involved in the clinical care of the patient. Once the airway is secured and the patient has reached a steady state of anesthesia, the main study intervention will then commence. We first would like to obtain the patient's average peak to peak interval for respiration at this steady state of anesthesia, as measured from the capnography. To do this, the research member in the room for data collection will use the iPhone stopwatch application and its 'lap button' feature to collect the respiration peak intervals (in seconds)

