12.0 Data Management

Descriptive statistics by treatment group will be evaluated for all demographic and procedural characteristics. The goal of the study is to determine if there is a significant difference in the change in respiratory response immediately following administration of saline or povidone-iodine solution in patients undergoing strabismus surgery. The primary outcome is the difference between the peak to peak interval time from the capnograph measured before saline or povidone-iodine administration versus after administration. Pre-exposure peak to peak interval will be measured as the average time between peaks for five breaths prior to administration. Post-exposure peak to peak interval will only be evaluated as the time between the two peaks at saline or povidone-iodine administration. Differences in the change in peak to peak interval time between the saline and povidone-iodine exposure groups will be evaluated using a linear regression approach. The model will include a treatment effect and will additionally control for patient age, history of prematurity, and use of any pre-medication to account for other factors thought to be associated with respiratory rate. We anticipate no change in peak to peak interval time in the saline group with variability of ± 4 seconds. A sample size of 50 patients per treatment group (100 patients total) provides $>80\%$ power to detect an increase in change in peak to peak interval of 2.5 seconds in the povidone-iodine group compared to the saline group assuming equal variance between the two groups using a 2-sided test with significance level set at alpha = 0.05. If the variability of the povidone-iodine group is larger, for example a variability of 8 seconds, compared to 4 seconds in the saline groups we still have 80% power to detect an increase in the povidone-iodine group of approximately 4 seconds.

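### The protocol allows for a doubled spread in the povidone-iodine arm but plans an ordinary regression under simple randomization, so in that scenario the type I error depends on the split the trial happens to get

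*Protocol*

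**What the plan says.** **Allocation.** Protocol Section 10.0: "This randomization will be determined using a simple randomization scheme provided by the study's statistician". No blocks, strata or fixed arm totals are mentioned.

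**Numbers.** Section 6.0: "We will enroll approximately 110 patients in this study to include 55 patients for each randomized" group. It then adds: "Please refer to section 12.0 for the justification behind this enrollment number". Section 12.0 supports a smaller figure: "A sample size of 50 patients per treatment group (100 patients total) provides" more than 80% power. The SAP repeats 50 per group. Neither document explains the step from 50 to 55. Section 14.0 provides for withdrawals but gives no rate.

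**Variance.** The base case in Section 12.0 is "We anticipate no change in peak to peak interval time in the saline group with variability of ± 4 seconds", with equal variance in both arms. The same paragraph then considers 8 s in the povidone-iodine arm against 4 s in the saline arm, and states that 80% power remains for a difference of about 4 s.

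**Analysis.** Section 12.0 compares the change in interval between arms by linear regression, adjusted for age, prematurity and premedication. The SAP instead describes a linear mixed model with a random subject effect and Bonferroni-corrected comparisons at each of 15 breaths. Neither document mentions arm-specific variances or robust standard errors.

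**The concern.** Ordinary regression estimates one residual variance and applies it to both arms. If the arms are the same size, the standard error of the treatment effect is right even when the true variances differ. If they are not, the pooled estimate leans towards the variance of the larger arm. A small arm with a large spread then gets too small a standard error and the test rejects too often; a large arm with a large spread makes the test too strict.

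The plan has both ingredients. Section 12.0 itself raises a twofold difference in SD, and simple randomization leaves the arm sizes to chance. A larger spread under povidone-iodine is plausible if some children respond with a long pause and others do not. The SAP's statement that no saline child had a change in respiration points the same way, although it gives no spreads and cannot settle the matter.

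At stake is whether a p-value near 0.05 on the primary comparison means what it says at the split the trial obtained.

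**Working it through.** **Inputs.** N = 110, 55 per arm planned (Section 6.0). SD 4 s in both arms with a 2.5 s difference, or SD 8 s against 4 s with a difference of about 4 s; 50 per arm; two-sided alpha 0.05 (all Section 12.0). Assumptions: variability means the SD of the change, errors are normal, simple randomization means independent 1:1 assignment, and covariates are ignored.

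**Step 1: the plan's own power figures.**
- Equal SD, 50/50: SE = 4 × √(2/50) = 0.80; 2.5/0.80 = 3.125; power = Φ(3.125 − 1.96) = 87.8% (87.2% by noncentral t). The claim of more than 80% is correct.
- SD 8 against 4, 50/50: SE = √(64/50 + 16/50) = 1.265; 4/1.265 = 3.162; power = Φ(3.162 − 1.96) = 88.5% (87.7% by Welch's t). Power of 80% is reached at about 3.6 s, which agrees with the protocol's rounded 4 s.

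**Step 2: what simple randomization gives.** Arm size is Binomial(110, 0.5), with SD √110/2 = 5.2.
- Exactly 55/55: 7.6%.
- Central 95% range: 45 to 65 per arm.
- At least one arm below 50: 29.4%; so both arms reach 50 in 70.6%, before any withdrawals.

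**Step 3: effect on base-case power.** At 45/65, SE = 4 × √(1/45 + 1/65) = 0.776 and 2.5/0.776 = 3.22, giving 89.1% by noncentral t. The value at 55/55 is 90.1%, and the mean over all splits is 89.9%.

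**Step 4: type I error of the pooled-variance test, SD 8 against 4, no true mean difference.** Let a and b be the povidone-iodine and saline arm sizes.
- True variance of the difference: T = 64/a + 16/b.
- Variance the regression uses, on average: P = {[(a−1)×64 + (b−1)×16]/108} × (1/a + 1/b).
- Approximate type I error: 2 × [1 − Φ(1.96 × √(P/T))].

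For 45/65: T = 1.422 + 0.246 = 1.668. The pooled variance is (44×64 + 64×16)/108 = 35.56, and P = 35.56 × 0.03761 = 1.337. √(P/T) = 0.895, the effective cut-off is 1.755, and the error is 0.079.

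| Povidone-iodine/saline | T | P | √(P/T) | Error, formula | Error, simulated |
|---|---|---|---|---|---|
| 45/65 | 1.668 | 1.337 | 0.895 | 0.079 | 0.080 |
| 50/60 | 1.547 | 1.385 | 0.946 | 0.064 | 0.064 |
| 55/55 | 1.455 | 1.455 | 1.000 | 0.050 | 0.051 |
| 60/50 | 1.387 | 1.548 | 1.057 | 0.038 | 0.040 |
| 65/45 | 1.340 | 1.671 | 1.117 | 0.029 | 0.030 |

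The simulation used 400,000 runs per split with t critical values.

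**Step 5: how often it matters.** By the formula, the error exceeds 0.06 when the povidone-iodine arm has 51 or fewer children (probability 25%) and is below 0.04 when it has 60 or more (20%). About 45% of splits therefore lie outside 0.04 to 0.06. Weighted over all splits, the error is 0.051.

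**Step 6: the remedy and its price.** With Welch's standard error and degrees of freedom, the simulated error is 0.050 to 0.051 at every split tried from 40/70 to 70/40 (200,000 runs each). If the SDs are in fact both 4 s, the Welch degrees of freedom at 45/65 are about 95 instead of 108. The critical value moves from 1.982 to 1.985, and power for 2.5 s stays at 89.1%.

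**The case against.** The best defence is that simple randomization is valid and the least predictable method, and that over repeated trials the test keeps its size: 0.051 on average, even in the unequal-variance scenario. Equal variance is the protocol's base case, and the 8 s figure is introduced only as an example when discussing power. The values 0.08 and 0.03 belong to splits at the edges of the 95% range. All of this is true. It means that the drift is conditional on the split and on unequal variances. It does not remove the point, because a trial is analysed at one known split.

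The SAP also describes a mixed model in place of the regression, so the figures above apply to the protocol's analysis only. That stands too, but the SAP states no arm-specific variance either, so nothing shows that the gap was closed.

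Three stronger readings are tempting and are not supported:
- *That 55 and 50 per arm contradict each other.* Enrolling about 110 exceeds the 100 that the calculation needs. The margin is unexplained, not inconsistent.
- *That chance imbalance endangers power.* An arm below 50 is fairly likely, but 80% power needs only about 42 per arm, and a 45/65 split still gives 89%.
- *That simple randomization is itself a fault.* Blocking is a reasonable preference, but in a single-centre trial with no blinding described, the added predictability is a real cost.

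**Conclusion.** The point holds as a conditional weakness in the analysis specification. If the SDs are 8 s and 4 s, as Section 12.0 contemplates, the nominal 5% regression test has a type I error between about 0.03 and 0.08 across the likely range of splits, and about 45% of splits fall outside 0.04 to 0.06. If the SDs are equal, there is no drift.

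The result rests on reading variability as an SD, normal errors, no covariates and unrestricted 1:1 allocation. If the statistician's list was in fact balanced, the split problem disappears. A reader might infer that the trial's overall false-positive rate is inflated, or that the SAP's results are distorted by these amounts. The first is not so, since the average is about 0.05; the second is unknown, because no error rate was computed for the mixed model. This is a cheap improvement worth making, not a threat to the trial's validity.

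**What to change.** **Main change.** In Protocol Section 12.0, state that the treatment effect will be tested with heteroscedasticity-robust standard errors (for example HC3) or a Welch-type method. In the SAP, let the mixed model have arm-specific variances, or use robust standard errors for its fixed effects. This takes one sentence in each document. The cost is a negligible loss of precision if the variances are equal. If enrolment is already complete, the change can still be made in the analysis, with the allocation method and the realised arm sizes reported beside it.

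**Optional.** Add a sentence to Section 6.0 or 12.0 explaining the step from 50 to 55 per arm. If the allocation list can still be changed, consider permuted blocks of varying, undisclosed size. These keep the arms close to equal at the price of slightly more predictability, and an incomplete last block can still leave a small imbalance.

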12.0 Data Management

Descriptive statistics by treatment group will be evaluated for all demographic and procedural characteristics. The goal of the study is to determine if there is a significant difference in the change in respiratory response immediately following administration of saline or povidone-iodine solution in patients undergoing strabismus surgery. The primary outcome is the difference between the peak to peak interval time from the capnograph measured before saline or povidone-iodine administration versus after administration. Pre-exposure peak to peak interval will be measured as the average time between peaks for five breaths prior to administration. Post-exposure peak to peak interval will only be evaluated as the time between the two peaks at saline or povidone-iodine administration. Differences in the change in peak to peak interval time between the saline and povidone-iodine exposure groups will be evaluated using a linear regression approach. The model will include a treatment effect and will additionally control for patient age, history of prematurity, and use of any pre-medication to account for other factors thought to be associated with respiratory rate. We anticipate no change in peak to peak interval time in the saline group with variability of ± 4 seconds. A sample size of 50 patients per treatment group (100 patients total) provides $>80\%$ power to detect an increase in change in peak to peak interval of 2.5 seconds in the povidone-iodine group compared to the saline group assuming equal variance between the two groups using a 2-sided test with significance level set at alpha = 0.05. If the variability of the povidone-iodine group is larger, for example a variability of 8 seconds, compared to 4 seconds in the saline groups we still have 80% power to detect an increase in the povidone-iodine group of approximately 4 seconds.

Several steps will be taken to ensure that the data collected for this study remains secure for the sake of the confidentiality of the patients enrolled. All study members are CITI certified and the anesthesia research staff have received Core Clinical Research Training (CCRT). Any data collected on the physical data sheet will not contain identifiers, but will rather contain the study ID number which is connected with patient identifiers on the study enrollment log saved on the secure research server. All data sheets are kept in a locked cabinet in the locked research office and all electronic data is stored in the study's secure REDcap database. All data will remain in the confines of MUSC and will be brought down for storage in the research office promptly after data collection.

13.0 Provisions to Monitor the Data to Ensure the Safety of Subjects (if applicable)

The Department of Anesthesia's Data Safety and Monitoring Board (DSMB) will review this study biannually. Any adverse events will be reported to the DSMB and IRB per policies in place. The members of the DSMB for the Department of Anesthesia and Perioperative Medicine are Drs. [name], [name], and [name]. These physicians are professors at MUSC who have engaged in clinical research throughout their careers.

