for 5 breaths. Specifically, at the patient's peak inspiration (as seen on the capnography), the study member will start the stopwatch and proceed to hit the 'lap' button for the next 5 consecutive inspiration peaks. These data intervals will be recorded on the data sheet after the 5 breaths are over, as the intervals are conveniently stored and numbered below the stopwatch in the app. We will do this to establish an average baseline respiratory rate for each individual patient. Next, patients who are randomized to Group A will receive three drops of povidone-iodine ophthalmic solution in each eye, with the right eye to receive the drops first. Group B will receive three drops in each eye of ophthalmic balanced salt solution. Similarly, the right eye will receive the drops first; the reason being that we know that there are differences in sympathetic stimulation on the right side of the face vs left (e.g. termination of supraventricular tachycardia) and although we don't know if this effects OCR, we chose to standardize right eye first. The eye drops will be administered by the study anesthesiologist. After application of either solution to the eyes of the patient, any change in ventilation can be detected and timed by observation of the capnography (end-tidal carbon dioxide) and direct observation of the chest wall with use of the iPhone stopwatch feature again. The capnograph is a standard monitor of respiration used during the administration of general anesthesia. Data collected at this time will include whether or not there was a change in respiration, what this change in respiration was, if assisted ventilation was required, how long assisted ventilation was required (if applicable), HR, BP, RR, SaO_2 , ETCO_2 , InspSevo, and ExpSevo. This study intervention and data collection will take less than 5 minutes and the surgical team will then progress with the case as they normally would.

Other data to be collected is as follows:

- Attending anesthesiologist and CRNA
- Age
- Weight
- Sex
- Co-existing diseases
- If the patient was a pre-term birth and if yes, the estimated gestational age at birth
- If premedication was given and if yes, what medication and dose
- If N_2O was used during inhalational induction

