14.0 Withdrawal of Subjects (if applicable)

Subjects will be withdrawn from the study if any changes need to be made to the anesthesia plan that do not align with the inclusion/ exclusion criteria of the study; e.g. if any airway intervention other than an LMA is required at the start of surgery.

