15.0 Risks to Subjects

The risks to the subjects are minimal. The anesthetics will be standard of care and the BSS and povidone-iodine ophthalmic solutions are commonly used eye surgery solutions that are safe for the application to the ocular surface in the manner in which we propose, as deemed by the FDA. These solutions are routinely used during strabismus surgery. As stated previously, the duration of the study intervention is very brief (seconds, to 4 minutes) and will cause minimal, if any, delay in the surgical procedure. If apnea becomes significant (e.g. arterial oxygenation saturation less than 94%, as measured by pulse oximetry), assisted or controlled ventilation is very easily provided via the LMA to counteract the apnea.

There is a risk of loss of confidentiality, but the anesthesia research team has safeguards in place for keeping patient health information secure and only accessed when absolutely necessary. All data will be stored on a secure server and consent and data forms will be held in a locked cabinet in a locked research office.

Though it is a randomized study, there is not a risk of randomization because neither of the possible groups poses any additional risk to the participants.

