Title: *The Effect of Povidone-iodine Ophthalmic Surgical Prep Solution on Respiration in Children Undergoing Strabismus Surgery with General Anesthesia*

NCT03349515

2018 August 15

Statistical Analysis: An *a priori* size calculation was conducted prior to the study. Assuming no change in the peak to peak end-tidal CO₂ interval time after drop instillation in the saline group, and a peak to peak interval time variability of ± 4 seconds, a sample size of 50 patients per group (100 patients total) provided $> 80\%$ power to detect an increase in change in peak to peak interval of 2.5 seconds in the povidone-iodine group compared to the saline group assuming equal variance between the two groups using a 2-sided test with significance level at $\alpha=0.05$.

Descriptive statistics by treatment group were estimated for patient and procedural characteristics. Differences in peak to peak interval time between the saline and povidone-iodine exposure groups were examined using a linear mixed model approach. Based on the *a priori* analysis plan, the model included fixed effects for treatment, breath number, a treatment by breath number interaction and a random subject effect to account for correlation between measures collected on the same subject. The model also controlled for factors thought to be associated with respiratory rate including age, pre-term birth, history of apnea, and breath duration prior to drop installation. Comparisons in breath duration between treatment groups at each of 15 breaths post-drop instillation were estimated from the model using Bonferroni corrected significance.

A secondary outcome of interest was occurrence of a significant change in respiration. Although apnea has been defined in the literature as a breath duration of 10 to 20 seconds, this definition is arbitrary and fails to account for within and between subject variability of breath duration. To account for within and between subject variability, we defined changes in respiration as having a breath duration greater than twice the inner-quartile range above the

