75th percentile for breaths within patient for the 10 breaths prior to and 15 breaths after instillation of drops. Associations between occurrence of change in respiration with patient and procedural characteristics were evaluated using univariate logistic regression models. Notably, no participants in the saline group experienced a change in respiration; therefore, all additional univariate tests were conducted on the subset of patients that received povidone-iodine drops. All analyses were conducted in SAS v.9.4 (SAS Institute, Cary NC, USA).

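### Must the plan say how a post-drop interval ended by an assisted breath is analysed?

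*Protocol*

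**What the plan says.** Protocol section 12.0 compares each child's mean interval over five breaths before the drops with one interval after them: "Post-exposure peak to peak interval will only be evaluated as the time between the two peaks at saline or povidone-iodine administration". It does not say what kind of breath must produce the second peak.

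Assistance is expected. Section 15.0 notes that "assisted or controlled ventilation is very easily provided via the LMA to counteract the apnea", with an oxygen saturation figure given only as an example. Section 10.0 lists the need for assisted ventilation and its duration among the data collected after the drops, and leaves its use to clinical judgement: "All decisions regarding anesthesia care, including the indication for preoperative pharmacologic anxiolysis, will be made by the attending pediatric anesthesiologist".

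The SAP goes further than one interval. "Comparisons in breath duration between treatment groups at each of 15 breaths post-drop instillation were estimated from the model", with Bonferroni correction. Its secondary outcome flags any breath that exceeds Q3 by more than two IQRs, where the reference is the child's own "75th percentile for breaths within patient for the 10 breaths prior to and 15 breaths after instillation of drops". Neither analysis mentions assisted breaths.

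Section 14.0 is the only nearby rule: "Subjects will be withdrawn from the study if any changes need to be made to the anesthesia plan that do not align with the" eligibility criteria. Its example is an airway other than a laryngeal mask at the start of surgery.

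**The concern.** The trial measures how long breathing pauses, and assistance ends a pause. An interval closed by an assisted breath is therefore a lower bound on the spontaneous pause. The SAP reports no change in respiration in any saline child, so such intervals would fall mainly in the povidone-iodine arm, among the strongest responders. A reader could not tell complete pauses from shortened ones.

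The secondary outcome adds a second difficulty. Assisted breaths are among the 25 values that set the child's own cut-off, so they could alter the classification of the child who received them. That flag is the outcome of all the SAP's logistic models.

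Finally, section 5.0 requires a plan of spontaneous ventilation. Read with section 14.0, that could be taken to mean that assisted children are withdrawn, which would remove the largest responses.

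**Working it through.** **1. The plan's own figures.** Inputs from section 12.0: 50 per arm, SD 4 s (taking the stated variability as an SD), difference 2.5 s, two-sided alpha 0.05.
- Equal SDs: SE = 4 × √(2/50) = 0.80 s; 2.5/0.80 = 3.125; power 87.2% (noncentral t, 98 df). The claim of more than 80% holds.
- SD 8 against 4: SE = √(64/50 + 16/50) = 1.265 s; 4/1.265 = 3.16; power 87.7% (Welch). Power of 80% is reached at about 3.6 s, so the plan's approximate 4 s is cautious.

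**2. A few intervals cut short.** The longest k povidone-iodine values are set to the next longest, and the arms are compared by an unadjusted two-sample test. The values of k are assumptions.

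| Case | k | Mean difference | Power |
|---|---|---|---|
| SD 4/4, 50 per arm | 0 | 2.50 s | 87% |
| | 2 | 2.43 s | 86% |
| | 5 | 2.31 s | 84% |
| SD 4/4, 55 per arm (section 6.0) | 5 | 2.32 s | 87% |
| SD 8/4, 50 per arm | 0 | 4.00 s | 88% |
| | 5 | 3.61 s | 84% |

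**3. A less favourable shape.** Suppose a quarter of povidone-iodine children respond by 16 s and the rest not at all, with noise SD 4 s. The mean is 0.25 × 16 = 4 s and the variance is 16 + 256 × 0.1875 = 64, so the SD is 8 s, matching the plan's unequal-variance case. The clock stops at a fixed excess over baseline.

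| Stopped at | Children cut, of 50 | Mean difference | Power |
|---|---|---|---|
| never | 0 | 4.00 s | 90% |
| +15 s | 7.5 | 3.46 s | 86% |
| +12 s | 10.6 | 2.91 s | 80% |
| +10 s | 11.9 | 2.47 s | 72% |

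The worst row loses (4.00 − 2.47)/4.00 = 38% of the effect. Nothing in the documents says which row applies.

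**4. Other handling rules, same mixture.** If assistance comes at +12 s, dropping assisted children leaves 0.5 s and 8% power. Timing instead to the next spontaneous breath, assumed 20 s later, gives 8.2 s. The literal rule in section 12.0 lies between these and errs only downwards.

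**5. Later breaths in the SAP series.** Assume 3 s spontaneous breaths and 10% to 25% of the arm assisted at a given breath. Assisted breaths of 2 s shift the contrast by (2 − 3) × 0.10 = −0.1 s to (2 − 3) × 0.25 = −0.25 s. Assisted breaths of 6 s shift it by +0.3 s to +0.75 s. The sign is open.

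**6. The cut-off, Q3 + 2 × IQR over 25 breaths.** Assume 2.5 s spontaneous breaths with 10% within-child variation.
- With one pause and no assisted breaths, the cut-off is about 3.3 s; with three slower assisted breaths, about 3.6 s.
- With one pause and six slower assisted breaths of length a, 7 of 25 values are slow. Q3, the 19th ordered value, becomes a and Q1 stays at b = 2.5 s. The cut-off is a + 2(a − b) = 3a − 2b: 3 × 4 − 5 = 7 s, or 3 × 5 − 5 = 10 s. Shorter pauses are then missed; longer ones are still flagged.
- In a child with no pause, one assisted breath of 4 s or 5 s is itself flagged in 93% or over 99% of simulations, against 7% to 8% with none.

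So the flag can be gained or lost.

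**7. Are assisted children kept?** Section 5.0 concerns the anesthesia plan before surgery. The section 14.0 example concerns an airway other than a laryngeal mask. Section 15.0 describes assistance through the mask as an expected response, and section 10.0 records it as post-drop data. Read together, assisted children stay in the analysis.

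**The case for a change.** The strongest case for a change is that the unrecorded part of the pause is the outcome itself, that it is lost mainly in one arm, and that the wrong handling rule could be damaging. Dropping assisted children could erase the effect, and timing to the next spontaneous breath could double it. One sentence and one censored-interval sensitivity analysis look cheap by comparison.

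Part of this stands. The loss cannot be called small without knowing how often and how early assistance was given. It cannot be called conservative outside the protocol's single interval. Counts of assisted and withdrawn children by arm would help a reader.

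The rest does not lead to a change. Both damaging rules need a reading that sections 10.0, 12.0 and 15.0 do not favour. A censored-normal model for the single interval would not touch the SAP's 15-breath mixed model. It recovers the truth on normal data with SD 4/4 (2.50 s, with 10% of povidone-iodine values capped), but not in the responder mixture with a true effect of 4 s. With a common SD it gives 3.5 s at a +12 s cap and 3.1 s at +10 s; with arm-specific SDs, 3.8 s and 3.4 s. It falls short where censoring would matter most.

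The SAP is also written in the past tense and reports a result, so a rule for marking assisted breaths prospectively would come late. The data sheet is not shown, so whether those breaths can be identified is unknown.

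**Conclusion.** No change to the plan is needed. This is missing detail that an analyst would fill sensibly: the interval ends at the next capnograph peak, and every child who received drops stays in the randomised arm. On that reading the observed interval is a fair measure under usual care. Assistance can shorten a recorded pause but not lengthen it, so it cannot produce a false lengthening.

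Under the plan's assumptions, up to 5 shortened intervals in 50 cost about 0.2 s of 2.5 s (0.4 s of 4 s with unequal SDs) and 4 percentage points of power. The loss reaches 38% of the effect only if nearly all responders are assisted by about 10 s above baseline. For the later breaths and the cut-off, the direction cannot be stated. A flag is lost only if there are at least six assisted breaths, they are slower than spontaneous ones, and the pause ended within roughly 6 to 10 s. A slow assisted breath can equally create a flag.

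These sizes rest on assumed responder shares, assistance times and breath lengths, none of which the documents give. The power figures use unadjusted two-sample tests in place of the protocol's regression, and the mixed model was not simulated. Counts by arm, and a check of the flags with assisted breaths left out, would be reasonable additions to the report but are optional.
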